4.3 Handling of Missing Data

All missing or partial data will be presented in the subject data listing as they are recorded on the Case Report Form (CRF) and the Bleeding Diary, respectively.

Date Mirena last known in situ (as defined in Section 4.7)

- If the day of the month of the date when Mirena threads were visible is missing, it will be imputed as the 15th of that month.
- If the date when Mirena threads were visible is missing (after possible imputation of a missing day), the date of Day 1 Year 6 will be used instead.
- If the day of the month of the date when Mirena location was found to be “In situ” or “Displaced, intrauterine” is missing, it will be imputed as the 15th of that month.
- If the date when Mirena location was found to be “In situ” or “Displaced, intrauterine” is missing (after possible imputation of a missing day), the date of Day 1 Year 6 will be used instead.

Stop date of study drug administration (as defined in Section 4.7)

- If the day of the month of the Mirena expulsion/removal date is missing and the subject was *not* pregnant during the extension treatment period, it will be imputed as the 15th of that month of Mirena expulsion/removal.
- If the day of the month of the Mirena expulsion/removal date is missing and the subject *was* pregnant during the extension treatment period, it will be imputed as follows:
 - If the subject was confirmed to be pregnant during that month (i.e. estimated date of conception during that month), the day of Mirena expulsion/removal will be imputed by the estimated day of conception.
 - If the subject was confirmed to be pregnant prior to that month (i.e. estimated date of conception prior to that month), the day of the Mirena expulsion/removal will be imputed by the first of that month of Mirena expulsion/removal.

- If the subject was confirmed to be pregnant after that month (i.e. estimated date of conception after that month), the day of the Mirena expulsion/removal will be imputed by the last of that month of Mirena expulsion/removal.
- If the Mirena expulsion/removal date is missing (after possible imputation of a missing day), the ‘date Mirena last known in situ’ will be used instead.

eDiary data

Missing bleeding diary data will be imputed following the sponsor’s Best Practice Document (BPD) on “Recording and Evaluation of Bleeding Data” (RD-SOP-1107) (1) and as described in Section 4.4, respectively.

Adverse event (AE) data

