The onset date of AEs is needed to distinguish treatment-emergent and pretreatment AEs. If the day of the month is missing, the last day of that month will be used for the derivations of the treatment emergent flag. If both day and month are missing December 31st will be used. Using this approach, AEs will always considered to be treatment emergent unless this can be ruled out.

Furthermore, the onset date of AEs is needed to distinguish between AEs in 6th / 7th / 8th year. If the day of the month is missing, the 15th of that month will be used for calculation of the year of onset. If both day and month are missing, July 1st will be used. If an upper or lower bound for the date is available (e.g. Day 1 Year 6), this date will be taken into account.

Pregnancy data: Pearl index (PI) calculation and cumulative failure rate

- Partially missing conception dates will be imputed by the minimum approach, i.e. the first possible on-treatment date (Day 1 Year 6) will be used.
- If the day of the month of the Mirena expulsion/ removal date is missing, it will be imputed as the 15th of that month.
- If the Mirena expulsion/ removal date is missing (after possible imputation of a missing day), the ‘date Mirena last known in situ’ will be used instead.

Time to expulsion/ perforation/ non-compliance

- If the day of the month of the date of expulsion/ perforation/ non-compliance is missing, it will be imputed as the 15th of that month.
- If the date of expulsion/ perforation/ non-compliance is missing (after possible imputation of a missing day), the ‘date Mirena last known in situ’ will be used instead.

Time to premature discontinuation

- If the day of the month of the date of premature discontinuation of study treatment is missing, it will be imputed as the 15th of that month.
- If the date of premature discontinuation of study treatment is missing (after possible imputation of a missing day), the date of the subject’s last scheduled or unscheduled visit prior to the end of treatment visit will be used.

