4.7 Data Rules

Start date of 'treatment period'

The date of baseline visit will be considered the start date of the 'treatment period', i.e. study day 1.

Start date of study drug administration, i.e. start date of 'extension treatment period'

Day 1 of Year 6 of Mirena use will be considered the start date of study drug administration.

Date Mirena last known in situ

The 'date Mirena last known in situ' is referred to in Integrated Protocol Section 10.3.2.1 and Integrated Protocol Table 10-1 and is needed to calculate the crude exposure time for PI calculation for subjects who were lost to follow-up (e.g. because the woman withdrew consent, was lost to follow-up, or died) and for ongoing subjects (during the analyses after Year 6 and Year 7).

The 'date Mirena last known in situ' will be the latest date when the subject was found to be compliant with Mirena, before the first occurrence of non-compliance (if any).

Compliance/non-compliance is described in Section 6.1.3.5 and Integrated Protocol Section 9.6.3.8.

Therefore, the 'date Mirena last known in situ' will be the latest of the following:

- Last date (before the first occurrence of non-compliance, if any) when Mirena threads were visible
- Last date (before the first occurrence of non-compliance, if any) when Mirena location was found to be "In situ" or "Displaced, intrauterine"

If any of these dates is missing or partial, it will be imputed individually as described in Section 4.3.

Stop date of study drug administration

If the Mirena was totally expelled or removed during the study, the stop date of study drug administration will be the date of Mirena expulsion or removal.

If the Mirena was not totally expelled or removed during the study (e.g. because the woman withdrew consent, was lost to follow-up, or died), the stop date of study drug administration will be the 'date Mirena last known in situ'.

For ongoing subjects (during the analyses after Year 6 and Year 7), the stop date of study drug administration will be the 'date Mirena last known in situ'.

Woman-years

One woman-year will comprise 365 days of study treatment exposure, unless otherwise stated.

Treatment-emergent AEs

The onset date of AEs will be used to distinguish between treatment-emergent and pre-treatment AEs. If an event occurred on Day 1 of Year 6 of Mirena use or later, it will be considered as treatment-emergent AE. Otherwise, it will be considered as pre-treatment AE.

AEs in 6th / 7th / 8th year

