The exact rules regarding how the crude exposure time will be calculated are given in Integrated Protocol Section 10.3.2.1 and Integrated Protocol Table 10–1 as well as in [Table 6–1](#) below.

Table 6–1: Definition of crude exposure times

PI	Reason for end of study/ continuation status	Crude exposure time
1-year PI (6th year)	Total expulsion	Date, when expulsion was discovered – Date of Day 1 Year 6 +1
	Partial Expulsion/ Mirena removal	Date of Mirena removal – Date of Day 1 Year 6 +1
	Pregnancy	Date of conception – Date of Day 1 Year 6 +1
	Lost to Follow-up	Maximum of (Date Mirena last known in situ – Date of Day 1 Year 6 +1; 1 day)
	Continues into 7th year of treatment	365 days
2-year PI (6th and 7th year)	Total expulsion	Date, when expulsion was discovered – Date of Day 1 Year 6 +1
	Partial Expulsion/ Mirena removal	Date of Mirena removal – Date of Day 1 Year 6 +1
	Pregnancy	Date of conception – Date of Day 1 Year 6 +1
	Lost to Follow-up	Maximum of (Date Mirena last known in situ – Date of Day 1 Year 6 +1; 1 day)
	Continues into 8th year of treatment	730 days
3-year PI (6th, 7th and 8th year)	Total expulsion	Date, when expulsion was discovered – Date of Day 1 Year 6 +1
	Partial Expulsion/ Mirena removal	Date of Mirena removal – Date of Day 1 Year 6 +1
	Pregnancy	Date of conception – Date of Day 1 Year 6 +1
	Lost to Follow-up	Maximum of (Date Mirena last known in situ – Date of Day 1 Year 6 +1; 1 day)
	Continues into 9th year of treatment	Minimum of (1095 days; Date of EOT visit – Date of Day 1 Year 6 +1)
Overall PI	Total expulsion	Date, when expulsion was discovered – Baseline visit date +1
	Partial Expulsion/ Mirena removal	Date of Mirena removal – Baseline visit date +1
	Pregnancy	Date of conception – Baseline visit date +1
	Lost to Follow-up	Maximum of (Date Mirena last known in situ – Baseline visit date +1; 1 day)
	Continued until EOT	Date of EOT visit – Baseline visit date +1

PI=Pearl Index; EOT=End of treatment

A pregnancy will be allocated to the time period(s) that are relevant for the calculation of the PIs described above, e.g., a pregnancy that occurs on day 400 will be relevant for the 7th year PI, the 2-year PI (6th & 7th year), the 3-year PI (6th, 7th & 8th year), and the overall PI. Pregnancies that occur before Day 1 Year 6 of Mirena use will not count for the 1-year PI, 2-year PI and 3-year PI. Pregnancies that occur after the Mirena was removed or an expulsion was discovered will not count for any PI calculation.

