It should be noted that pregnancies that occur within 7 days after the end of exposure will count for the PI calculations.

Furthermore, it should be noted that pregnancies that occur after partial expulsion or first occurrence of non-compliance but before Mirena removal will count for the PI calculations.

Exposure times to be subtracted for Pearl index analyses:

Subjects who apply backup contraception are not at risk or are at lower risk of getting pregnant than subjects who do not apply backup contraception. In case a subject uses backup contraception (e.g., condoms to prevent sexually transmitted disease), the respective 28-day reference period(s) of backup contraception use will be excluded from the exposure time, unless a pregnancy occurred in that 28-day reference period. In the Pearl index analyses, the first 28-day reference period will start at Day 1 Year 6. Missing data will be considered as no use of backup contraception.

Primary analysis:

The primary method for the evaluation of the occurrence of pregnancy is the PI defined as the number of pregnancies per 100 woman-years.

The PIs and the corresponding 2-sided 95% confidence interval (CI) will be calculated using the model specified below.

Mathematical model for the calculation of the PI:

By assuming that the number of pregnancies follows a Poisson-distribution, the point estimate and the 95% CI for the PI can be calculated as follows:

$$PI = x/E,$$

$$\text{lower 95\% confidence limit of PI} = 0.5 \times \chi^2_{(0.025, 2x)} / E$$

$$\text{upper 95\% confidence limit of PI} = 0.5 \times \chi^2_{(0.975, 2(x+1))} / E$$

where x = number of pregnancies,

E = exposure in 100 woman-years,

$\chi^2_{(\alpha, df)}$ is the alpha-quantile from χ^2 -distribution with df degrees of freedom.

All PIs described above will also be presented by parity (no births vs. at least one birth), BMI (<30 kg/m² vs. ≥30 kg/m²) and age at insertion (<18 years vs. 18-25 years vs. 26-35 years, and <18 years vs. 18-35 years), age at baseline (18-25 years vs. 26-35 years vs. >35 years, and 18-35 years vs. >35 years), race and ethnicity. The age at insertion will be calculated as: age at baseline (recorded on the eCRF at baseline, Visit 2) minus 5 years.

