To assess pregnancies with regard to subgroup combinations, e.g. by age and parity, a listing on all pregnancies providing detailed information regarding subject number, age, parity, date of Mirena insertion, date of baseline visit, date of Day 1 Year 6 of Mirena use, date of Mirena removal, (estimated) date of (partial/total) expulsion, estimated date of conception, location of pregnancy implantation at time of diagnosis, and estimated date of conception relative to Mirena insertion/ relative to Day 1 Year 6 of Mirena use/ relative to stop date of study drug administration will be provided.

Secondary analysis:

In order to fulfill the European guideline EMEA-‘Guideline on clinical investigation of steroid contraceptives in women’ (EMEA/CPMP/EWP/519/ Rev1, July 2005.) (2), the cumulative failure rate, i.e. the probability of getting pregnant will be calculated using the Kaplan-Meier method in addition to calculation of the different PIs.

Periods of backup contraception use will not be subtracted from the exposure time.

Sensitivity analysis:

The usual assumption for the calculation of the PI is a constant hazard for the event of becoming pregnant over time. As this cannot necessarily be assumed for the study treatment of this study, PIs will be calculated *per year*, as sensitivity analyses.

Similar analyses (PIs and cumulative failure rates) will be provided for ectopic pregnancies.

Sensitivity analysis (introduced post-hoc after Year 6 database lock, prior to Year 7 database lock):

The primary analysis (‘1 year PI (sixth year)’ after Year 6 database lock based on the PAS Year 6) was conducted using the following rules:

- 1 WY = 365 days
- Complete and incomplete 28-day cycles are used for the exposure calculation (i.e., the days of the last 28-day cycle are used even if incomplete)

A sensitivity analysis will be conducted using the following rules

- 1 WY = 13 28-day cycles (i.e., 364 days)
- Only complete 28-day cycles are used

Similar analyses will be performed after Year 7 and Year 8 database lock, i.e. ‘2 year PI (sixth and seventh year)’ after Year 7 database lock based on the PAS Year 7 and ‘3 year PI (sixth, seventh and eighth year)’ after Year 8 database lock based on the PAS Year 8, respectively. PIs will be also be calculated *per year*, i.e. ‘Year 6 PI’ and ‘Year 7 PI’ after Year 7 database lock based on the PAS Year 7 and ‘Year 6 PI’, ‘Year 7 PI’ and ‘Year 8 PI’ after Year 8 database lock based on the PAS Year 8.

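### SAP 4.3 imputes a missing removal or expulsion day in two ways for a woman who conceived, and the rule assigned to the Pearl Index can drop a pregnancy that the SAP's own stop-date rule would count

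*SAP*

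**What the plan says.** SAP 4.3 deals twice with a removal or expulsion date whose month is known and whose day is missing.

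- **Stop date of study drug administration, pregnant woman.** If conception fell in the removal month, "the day of Mirena expulsion/removal will be imputed by the estimated day of conception". If it fell in an earlier month, "the day of the Mirena expulsion/removal will be imputed by the first of that month of Mirena expulsion/removal". If it fell in a later month, "the day of the Mirena expulsion/removal will be imputed by the last of that month of Mirena expulsion/removal".
- **PI and cumulative failure rate.** "If the day of the month of the Mirena expulsion/ removal date is missing, it will be imputed as the 15th of that month", with no condition on pregnancy.

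These are not two different dates. When the device was expelled or removed, SAP 4.7 states that "the stop date of study drug administration will be the date of Mirena expulsion or removal".

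Two statements in SAP 6.2.1 then decide whether a pregnancy counts: "Pregnancies that occur after the Mirena was removed or an expulsion was discovered will not count for any PI calculation", but "pregnancies that occur within 7 days after the end of exposure will count for the PI calculations". The same section plans a listing of all pregnancies that includes the conception date "relative to stop date of study drug administration will be provided".

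**The concern.** For a woman with a counted pregnancy, exposure ends at conception (SAP Table 6–1), so her removal date hardly affects the denominator. It does decide whether she enters the numerator. The conception-aware rule never places removal before a conception in the same month. The flat 15th can do so, although the conception date is known.

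Two things are at stake. First, the less conservative of the sponsor's own two rules is assigned to the primary endpoint. The bullet just above it takes the opposite attitude and moves partly missing conception dates onto treatment. Second, the listing could show a conception on the stop day for a pregnancy that the PI has left out as post-removal.

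**Working it through.** **Inputs.** The two imputation rules (SAP 4.3); the counting rule of removal plus 7 days (SAP 6.2.1); expected exposure of 832 woman-years and a true PI of 0.2 or 0.3 (Protocol 10.4); the exact Poisson limits (SAP 6.2.1).

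**Plan's own figures.** The upper limit is 0.5 × χ²(0.975, 2(x+1)) / E, with E = 8.32. It is 0.868 at x = 2 and 1.054 at x = 3, so it stays at or below 1 when x ≤ 2. P(X ≤ 2) is 76.7% with mean 0.2 × 8.32 = 1.66, and 54.5% with mean 0.3 × 8.32 = 2.50. Protocol 10.4 states 76% and 55%, so the figures reproduce.

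**Which conceptions change status.** The removal month is known, the removal day is missing and the conception date is complete.

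| Conception | Stop-date rule: removal day, counts? | Flat 15th: counts? |
|---|---|---|
| Earlier month | 1st, yes | yes |
| Removal month, days 1–15 | conception day, yes | yes |
| Removal month, days 16–22 | conception day, yes | yes (1–7 days after the 15th) |
| Removal month, day 23 to end | conception day, yes | **no** (8 or more days after) |
| Next month, days 1–7 | last day, yes (1–7 days after) | **no** |
| Next month, day 8 or later | last day, no | no |

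Example: conception on the 25th, true removal on the 28th, day not recorded. The PI rule gives removal on the 15th, 25 − 15 = 10 days before conception, so the pregnancy is excluded. The stop-date rule gives the 25th, so it counts, and the listing shows conception on the stop day.

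**Share of truly on-treatment conceptions lost.** Assume that conception day c and removal day r are uniform within one month of L days. On-treatment pairs (c ≤ r) number L(L+1)/2. Lost pairs have c ≥ 23.

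- L = 30: (8 + 7 + … + 1) / 465 = 36/465 = 7.7%
- L = 31: (9 + 8 + … + 1) / 496 = 45/496 = 9.1%
- L = 28: (6 + 5 + … + 1) / 406 = 21/406 = 5.2%

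**Errors of each rule against the true dates.** In a 30-day month, a pregnancy should count when conception is no later than removal plus 7 days.

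- Flat 15th: wrongly drops 92 same-month pairs and 28 next-month pairs (days 1–7), 120 in all. It wrongly counts 105 pairs, with early removal and conception more than 7 days later but by the 22nd.
- Stop-date rule: drops none. It wrongly counts 900 − 647 = 253 same-month pairs (647 of the 900 should count) and 7 × 30 − 28 = 182 next-month pairs (days 1–7).

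**Effect of one event at 832 woman-years.**

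- x = 3: PI = 3/8.32 = 0.361, upper limit 1.054
- x = 2: PI = 2/8.32 = 0.240, upper limit 0.868

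**The case against.** The strongest reply is that the stop-date rule is a worst-case convention, not the truth. Relative to that rule the flat 15th can only remove pregnancies, and a reader might infer that the PI is biased in the product's favour. The documents do not support this. Against the true dates, with uniform days in a 30-day month, the 15th makes 120 wrong exclusions and 105 wrong inclusions, which is roughly balanced. The stop-date rule errs in one direction only, by counting too many. This part of the objection stands.

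Three other stronger readings also fail.

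- **Share lost.** Days from the 23rd onward are 6/28 = 21%, 8/30 = 27% or 9/31 = 29% of a month. These are shares of calendar days. Many conceptions on those days would truly follow removal.
- **Expulsions discovered late.** For total expulsion, Table 6–1 uses the discovery date, so late discovery does not in itself make that date uncertain. Scheduled removals take place at the end-of-treatment visit (Protocol 9.2.9). The realistic route is mainly removal outside study procedures, which Protocol 6.4.1 names as a withdrawal reason.
- **Crossing 1.** Protocol 10.4 uses an upper limit of 1 to describe the sample size. It is not a success criterion.

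It is also fair that a dropped case could be noticed, because the listing shows removal and conception dates and partial dates are listed as recorded. That limits undetected loss but does not settle which date governs the count. The balance of errors likewise does not justify giving one event two dates.

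**Conclusion.** The inconsistency is real, and it reaches the numerator of the primary endpoint. One partial date receives two imputations, no text reconciles them, and the one assigned to the PI is less conservative than the sponsor's own rule for the stop date. It is not shown to be biased in one direction against the true dates.

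The trigger is narrow: a known removal month, a missing day, and a complete conception date from day 23 of that month to day 7 of the next. Given a missing day and an on-treatment conception in the removal month, about 5% to 9% would be lost. That figure assumes uniform days. The documents give no frequency for missing days, so no overall expected loss can be stated.

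The case is worth settling because expected counts are so low. At a true PI of 0.2 about 1.7 pregnancies are expected over three years, so one disputed event visibly moves both the estimate and its upper limit. The same SAP paragraph also governs the cumulative failure rate. If that analysis counts events as the PI does, it is affected in the same way.

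**What to change.** In the SAP 4.3 paragraph on the PI and cumulative failure rate, cross-refer to the three-branch stop-date rule for women with a pregnancy, and keep the 15th only for women without one. A single removal date then governs the PI, the Kaplan-Meier failure rate and the pregnancy listing.

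The cost is one sentence in the SAP and one derivation in the program. There is also a statistical cost. The stop-date rule will count some conceptions that truly occurred more than 7 days after removal, so the PI may come out higher than the true dates warrant. To make this visible, list any pregnancy whose counting depends on an imputed removal day, and report the PI with and without it.

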4.4 Handling of Missing Bleeding Intensities and Censored eDiaries

Uterine bleeding data will be handled according to the sponsor's BPD "Recording and evaluation of bleeding data" (RD-SOP-1107) (1).

Up to two consecutive days of missing bleeding intensities will be replaced using a worst case approach during the evaluations. That is, the missing bleeding intensity will be replaced by the maximum of the bleeding intensities of the day before and the day after the missing day(s). If three or more consecutive days are missing bleeding intensities, the entire reference period is to be considered invalid/missing for the analyses.

Up to five days of missing bleeding intensities per 90-days reference period will be replaced. If more than five days are missing bleeding intensities, the entire 90-days reference period is to be considered invalid/missing for the analyses.

Up to two days of missing bleeding intensities per 28-days reference period will be replaced. If more than two days are missing bleeding intensities, the entire 28-days reference period is to be considered invalid/missing for the analyses.

A diary that ends before the end of the reference period will still be evaluated if it is at least two thirds of the length of the reference period. The bleeding pattern indices incorporating the length of an event, such as mean length of the bleeding episodes, will be calculated as for a complete diary. However, the bleeding pattern indices incorporating the number of days or the number of events will be corrected in order to account for the shorter length of the diary. The correction factor is the length of the reference period divided by the length of the diary. For example, 15 days of bleeding recorded in the diary that was kept 75 days instead of the 90 days of the entire reference period will be adjusted to $15 \times (90 / 75) = 18$ days. This rule assumes that the observed average number of bleeding days ($15 / 75$) stays constant in the reference period ($15 / 75 = 18 / 90$).

